APPENDIX C: Cockcroft-Gault estimation of CrCl:

Cockcroft-Gault estimation of creatinine clearance (CrCl):

(Cockcroft, 1976; Luke 1990)

$$\text{CrCl (mL/min)} = \frac{(140 - \text{age}) \times (\text{weight, kg})}{72 \times (\text{serum creatinine, mg/dL})}$$

(Males)

$$\text{CrCl (mL/min)} = \frac{(140 - \text{age}) \times (\text{weight, kg})}{72} \times 0.85 \times (\text{serum creatinine, mg/dL})$$

(Females)

**MEMORIAL SLOAN-KETTERING CANCER CENTER
IRB PROTOCOL**

IRB#: 11-107A(12)

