The metabolic profile of lenalidomide in humans has not been studied. In healthy volunteers, approximately two-thirds of lenalidomide is eliminated unchanged through urinary excretion. The process exceeds the glomerular filtration rate and therefore is partially or entirely active. Half-life of elimination is approximately 3 hours.

MEMORIAL SLOAN-KETTERING CANCER CENTER
IRB PROTOCOL

IRB#: 11-107A(12)

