6.0 CRITERIA FOR SUBJECT ELIGIBILITY

6.1 Subject Inclusion Criteria

Patients fulfilling the following criteria will be eligible for entry into this study:

- Patients must be 18 years of age or above at the time of enrollment.
- Patients must show evidence of *asymptomatic* relapse and/or progression of disease (increasing M spike in serum or urine by consensus criteria) while on lenalidomide maintenance after HDM/ASCT as part of initial line of therapy. Patients who have not had an HDM/ASCT as part of initial line of therapy but who are on continuous/maintenance lenalidomide after initial therapy will be permitted on study.
- Patient must have myeloma that is measurable by either serum or urine evaluation of the monoclonal component or by assay of serum free light chains. Measurable disease is defined as one or more of the following: serum M-protein ≥ 0.5 g/dl, urine M-protein ≥ 200 mg/24 h, and/or serum FLC assay: involved FLC level > 10 mg/dL with abnormal serum FLC ratio.
- Patients must have adequate organ function including: Hepatic function with Bilirubin $< 2x$ the upper limit of normal and ALT and AST $< 3x$ the upper limit of normal; renal function with creatinine clearance ≥ 60 ml/min using the Cockcroft-Gault formula; hematologic function as defined by an absolute neutrophil count > 1000 neutrophils per microliter, platelet $> 50,000$ platelets per microliter and hemoglobin of ≥ 9 gm/dL without transfusion support.
- All study participants must be registered into the mandatory Revlimid REMS® program, and be willing and able to comply with the requirements of the REMS® program.
- Females of child bearing potential (FCBP)¹ must adhere to the scheduled pregnancy testing as required in the Revlimid REMS® program. FCBP must have a negative serum

¹ A female of childbearing potential is a sexually mature female who: 1) has not undergone a hysterectomy or bilateral oophorectomy; or 2) has not been naturally postmenopausal for at least 24 consecutive months (i.e., has had menses at any time in the preceding 24 consecutive months).

MEMORIAL SLOAN-KETTERING CANCER CENTER IRB PROTOCOL

IRB#: 11-107A(12)

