8.0 PRETREATMENT EVALUATION

The following tests will be done within 7 days prior to enrollment:

- Mandatory pregnancy test, serum or urine HCG (sensitivity of at least 50 mIU/mL) for FCBP.

Women are required to have 2 pregnancy tests prior initiation of lenalidomide as follows (Appendix B):

- The first is required within 10 to 14 days prior to prescribing lenalidomide
- The second within 24 hours of prescribing lenalidomide and prescription must be filled within 7 days.

The following tests will be done within 14 days prior to enrollment:

- History and physical exam including vital signs, height, weight, performance status, and toxicity assessment using CTCAE 4.0.
- Serum M-spike studies: Serum protein electrophoresis (SPEP), serum immunofixation (IF) and quantitative immunoglobulins, and serum free light chain assay
- Urine M-spike studies: Twenty-four hour urine for total volume and total protein (TV, TP), immunofixation (IF), protein electrophoresis (UPEP), N-telopeptides and creatinine clearance using the Cockcroft-Gault formula
- Comprehensive Metabolic Panel (includes Albumin, Alkaline Phosphatase, ALT, AST, BUN, Calcium, Carbon dioxide, Chloride, Creatinine, Glucose, Potassium, Sodium, Total Bilirubin, Total Protein), beta2-microglobulin, C-reactive protein, LDH
- CBC with differential
- INR/PTT, BNP, and troponin.
- Electrocardiogram (EKG)
- Mandatory pregnancy test, serum or urine HCG (sensitivity of at least 50 mIU/mL) for FCBP.

Women are required to have 2 pregnancy tests prior initiation of lenalidomide as follows

MEMORIAL SLOAN-KETTERING CANCER CENTER
IRB PROTOCOL

IRB#: 11-107A(12)

(Appendix B):

- o The first is required within 10 to 14 days prior to prescribing lenalidomide
- o The second within 24 hours of prescribing lenalidomide and prescription must be filled within 7 days.

The following tests will be performed within 56 days prior to patient enrollment:

- Hepatitis A, B, C serologies and HIV I/2 test
- A skeletal survey that should be reviewed at MSKCC or the participating site if not performed at MSKCC or the participating site. (Please note: the skeletal survey is not required if a PET scan has been completed)
- PET scan or total body MRI if available (optional)

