Appendix C: Cockcroft-Gault Estimation Of Crcl

Appendix D: Medication Diary/Log For Lenalidomide And Dexamethasone

Appendix E: ECOG Performance Status

APPENDIX A: CRITERIA FOR SYMPTOMATIC AND ASYMPTOMATIC RELAPSE AND PROGRESSION OF MULTIPLE MYELOMA

Patients will be considered as having *symptomatic* relapse/progression of disease if they show evidence of disease relapse or progression by serum or urine studies according to consensus criteria, AND present any of the following organ dysfunctions that are deemed to be related to disease progression:

- [C] Calcium elevation in the blood (serum calcium > 10.5 mg/l or upper limit of normal)
- [R] Progressive renal insufficiency (serum creatinine > 2mg/dl)
- [A] Progressive anemia with hemoglobin < 9 g/dl

- [B] New lytic lesion by skeletal survey

Patients will be considered as having asymptomatic relapse/progression if they show evidence of disease relapse or progression by serum or urine studies according to consensus criteria without evidence of organ damage as defined above.

APPENDIX B: LENALIDOMIDE RISKS OF FETAL EXPOSURE, PREGNANCY TESTING GUIDELINES AND ACCEPTABLE BIRTH CONTROL METHODS

Risks Associated with Pregnancy

The use of lenalidomide in pregnant females and nursing mothers has not been studied nor has the effect of the lenalidomide on human eggs and sperm. Lenalidomide is structurally related to thalidomide. Thalidomide is a known human teratogenic active substance that causes severe life-threatening birth defects. An embryofetal development study in animals indicates that lenalidomide produced malformations in the offspring of female monkeys who received the drug during pregnancy. The teratogenic effect of lenalidomide in humans cannot be ruled out. Therefore, a risk minimization plan to prevent pregnancy must be observed.

All study participants must be registered into the mandatory Revlimid REMS™ program, and be willing and able to comply with the requirements of Revlimid REMS™.

Criteria for females of childbearing potential (FCBP)

This protocol defines a female of childbearing potential as a sexually mature female who: 1) has not undergone a hysterectomy or bilateral oophorectomy or 2) has not been naturally postmenopausal for at least 24 consecutive months (i.e., has had menses at any time in the preceding 24 consecutive months).

The investigator must ensure that:

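### As extracted, Appendix C's creatinine clearance formula for women multiplies by serum creatinine where the men's formula divides by it; check the page and reconcile the two lines.

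*Combined protocol and SAP*

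**What the plan says.** Section 6.1 requires "renal function with creatinine clearance ≥ 60 ml/min using the Cockcroft-Gault formula". Section 8.0 lists "creatinine clearance using the Cockcroft-Gault formula" among the tests due within 14 days before enrollment. Neither section points to Appendix C, but it is the only place in the document where the formula is written out.

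Appendix C gives two lines, one for men and one for women. Both start with 140 minus age, times weight in kilograms. In the men's line the denominator is "72 \times (\text{serum creatinine, mg/dL", so creatinine divides. In the women's line, as extracted, the denominator contains 72 alone, and the factor 0.85 and the creatinine follow the fraction as multipliers: "72} \times 0.85 \times (\text{serum creatinine, mg/dL".

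Section 5.1.1 states that in healthy volunteers "approximately two-thirds of lenalidomide is eliminated unchanged through urinary excretion". Appendix A, which Section 6.2 uses to exclude symptomatic progression, has a separate renal item: "Progressive renal insufficiency (serum creatinine > 2mg/dl".

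**The concern.** The two lines cannot both be right. Estimated clearance falls as creatinine rises in men, but rises with it in women. The contradiction is visible inside the appendix and needs no outside source.

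The formula feeds the protocol's only clearance threshold for entry. If someone computed a woman's clearance from the appendix as it reads, a raised creatinine could carry her over 60 mL/min and a low one could keep her out. Because the drug is largely cleared by the kidney, the first of these is a safety matter as well as an eligibility error. Section 7.0 expects 38 of the 53 patients from collaborating centers, so the written formula should leave no room for different readings.

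**Working it through.** The plan gives no worked clearance value, so there is no figure to reproduce. The check is to evaluate the women's line in its possible forms and compare each with the threshold.

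**Inputs from the documents:** the two lines of Appendix C and the 60 mL/min threshold of Section 6.1.

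**Assumed inputs:** the ages, weights and creatinine values below are illustrative and do not come from the documents. They span 50 to 70 years, 60 to 80 kg and 0.7 to 2.0 mg/dL.

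**Formulas.** Let K = 0.85 × (140 − age) × weight / 72, and let Cr be serum creatinine in mg/dL.

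- As extracted: clearance = K × Cr.
- Creatinine in the denominator, as for men, with 0.85 applied to the whole fraction: clearance = K / Cr.
- Ratio of the two: (K × Cr) / (K / Cr) = Cr². They agree only at Cr = 1.0.

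For 65 years and 65 kg, K = 0.85 × 75 × 65 / 72 = 57.6. At Cr 1.5 the extracted line gives 57.55 × 1.5 = 86.3, and division gives 57.55 / 1.5 = 38.4. The other rows follow in the same way.

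| Assumed woman | K | Cr | As extracted | Divided | Against 60 mL/min |
|---|---|---|---|---|---|
| 65 y, 65 kg | 57.6 | 1.5 | 86.3 | 38.4 | passes / fails |
| 65 y, 65 kg | 57.6 | 2.0 | 115.1 | 28.8 | passes / fails |
| 60 y, 60 kg | 56.7 | 0.7 | 39.7 | 81.0 | fails / passes |
| 50 y, 80 kg | 85.0 | 0.8 | 68.0 | 106.2 | passes both |
| 70 y, 65 kg | 53.7 | 1.0 | 53.7 | 53.7 | fails both |

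**Where the two forms part.** The extracted line passes a woman when Cr ≥ 60/K. Division passes her when Cr ≤ K/60.

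- 65 y, 70 kg (K = 62.0): extracted Cr ≥ 0.97, divided Cr ≤ 1.03.
- 50 y, 80 kg (K = 85.0): extracted Cr ≥ 0.71, divided Cr ≤ 1.42. She passes both ways between 0.71 and 1.42.
- 70 y, 65 kg (K = 53.7): extracted Cr ≥ 1.12, divided Cr ≤ 0.90. She fails both ways between those limits.

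The direction of the test is reversed, but the classification changes only for women outside the band around Cr = 1.0 where the two forms agree.

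**A third layout.** If 72, 0.85 and creatinine were all under the bar, the direction would be right, but 0.85 would raise the women's value above the men's. At 65 y, 70 kg and Cr 1.0 the men's line gives 75 × 70 / 72 = 72.9, and this layout gives 72.9 / 0.85 = 85.8. Finding creatinine under the bar is therefore not enough to close the point; the position of 0.85 must be checked too.

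**The case against.** The strongest reply is that the protocol page may contain no error. The text was read from PDF by a program, and everything turns on where that program ended the denominator. The women's line has the same elements in the same order as the men's, with only 0.85 inserted. A correct fraction with the factor set beside it could be flattened into what we see. The same extraction has damaged layout elsewhere: the neutrophil threshold in Section 9.3 appears to have lost a superscript. This stands, and it makes the point conditional on the source page.

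The second reply is that Sections 6.1 and 8.0 call for a standard formula by name and do not send the reader to Appendix C, although the protocol does cite Appendix A in Section 6.2 and Appendix B in Section 8.0. A site using an ordinary calculator would be unaffected. This also stands.

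Third, other checks exist. Section 15.1.1 has collaborating sites send laboratory results for central review before registration. The assessment schedule lists creatinine clearance under the 24-hour urine studies. Appendix A flags creatinine above 2 mg/dL. These reduce the risk but do not remove it: the Appendix A item covers only progressive insufficiency related to the disease and would miss the example at 1.5 mg/dL.

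Fourth, it may be said that the documents do not settle where 0.85 belongs. That has less force. The extracted line already has 0.85 multiplying the fraction, so moving creatinine alone into the denominator, as in the men's line, gives the men's expression times 0.85.

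**Conclusion.** As extracted, Appendix C is internally inconsistent: creatinine multiplies for women and divides for men. Used literally, the women's line is wrong by a factor of creatinine squared relative to division and would misclassify some women, in both directions, against the 60 mL/min criterion. The sizes shown rest on assumed patients.

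A reader might infer that the renal entry test runs backwards for women throughout the trial, or that women were wrongly admitted or turned away. The documents do not support either. The criterion names the formula and not the appendix, some women are classified alike by both forms, the eligibility checklist is not among the documents, and nothing shows that any site computed from Appendix C.

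The point is therefore a conditional correction, to be verified on the page first. It becomes serious only if the page confirms the misprint. It has no statistical consequence: clearance does not enter the sample size, the error rates or the rule of 12 responders in 53.

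**What to change.** Check Appendix C in the source PDF. If it already shows creatinine in the denominator with 0.85 applied to the whole fraction, nothing needs changing. Otherwise reconcile the women's line with the men's as [(140 − age) × weight / (72 × serum creatinine)] × 0.85. A cross-reference to Appendix C from Sections 6.1 and 8.0 would then make clear which expression applies.

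Only if the misprint is confirmed, ask whether any site or the eligibility checklist used the printed line. If so, recheck the recorded clearances of the women concerned.

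The cost is a look at one page, at most a one-line correction with its cross-references, and, if the misprint was used, a short review of screening records. The design and analysis do not change.

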APPENDIX D: Pill Diary for IRB #11-107

Number of Pills Given: _____
 Total Daily Dose: _____
 (To be Completed by RN)

Pill Bottle(s) returned: Circle **Yes** or **No**
 Number of Pills **returned**: _____

PLEASE FILL OUT AND BRING THIS SHEET AT YOUR NEXT VISIT. This log should be completed each time you take the study medication at home, and returned at the end of each cycle. If you miss a dose, please indicate in the table below.

CYCLE #: _____ # of WEEKS _____

Day	Date	Number of Lenalidomide capsules taken (please indicate time)	Dexamethasone tablets taken (please indicate time)
EXAMPLE	1/1/2011	2, 4:00 PM	1, 3:00 PM
1			
2			
3			
4			
5			
6			
7			
8			
9			
10			
11			
12			
13			
14			
15			
16			
17			
18			
19			
20			
21			
22			
23			
24			
25			
26			
27			
28			

Patient Signature: _____ Date: _____

Consenting Professional/Research RN Signature: _____ Date: _____

Consenting Professional/Research RN
 Comments: _____

MEMORIAL SLOAN-KETTERING CANCER CENTER
IRB PROTOCOL

IRB#: 11-107A(12)

APPENDIX E: ECOG Performance Status

Grade	Description
0	Normal activity, fully active, able to carry on all pre-disease performance without restriction
1	Symptoms, but fully ambulatory, restricted in physically strenuous activity but ambulatory and able to carry out work of a light or sedentary nature (e.g. light housework, office work)
2	Ambulatory and capable of all self-care but unable to carry out any work activities. Up and about more than 50% of waking hours.
3	Capable of only limited self-care, Confined to bed or chair more than 50% of waking hours.
4	Completely disabled. Cannot carry on any self-care. Totally confined to bed or chair.
5	Death
